9.6 Data Analyses

Data Evaluation:

Prior to conducting the analyses outlined below, we will evaluate the statistical properties of our baseline information and outcome measures. Descriptive statistics, including measures of central tendency (means, medians, other percentiles) and dispersion (standard deviations, ranges) will be computed for continuous data such as the age at enrollment, PEG composite score and other continuous measures. We will also check for potential outliers, normality and missing data. Frequency distributions will be calculated for categorical data such as sex.

We will compare the distributions of baseline characteristics between the two groups to assess the effectiveness of the randomization. All analyses for treatment group comparisons will use the original treatment assignment as randomized for each participant (intent-to-treat). We will adjust for any baseline variable that either statistically (based on a p-value cutoff of $p < 0.2$) or clinically differs between the two groups. Data transformations may be applied to outcomes depending on the shape of the distribution to better approximate normality. We will consider ease of interpretation and clinical meaningfulness when choosing transformations.

Aim 1: To integrate and test an evidence-based mindfulness clinical pain program, OPTIMUM, for patients with cLBP in the primary care setting.

Primary Hypothesis: patients in OPTIMUM will have significantly **improved pain intensity and interference as measured by the PEG composite score** at completion of the program and 6 months (primary end point) and 12-months later, as compared to PCP Usual Care.

We will compare the PEG (primary outcome) at T2 (8 weeks from baseline) and T3 and T4 (6 months and 12 months from T2) with PEG at T1 (baseline) included in the vector of repeated measures using a mixed effects model. We will include the intervention group indicator, time

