and their interaction as fixed effects, with random effects for repeated measures on individuals over time and random class effects for group in the intervention arm. We are proposing to control for clustering effect within each class using a random effect because the response of participants in the same class might be correlated. In the study by [name], the intraclass correlation coefficient for the class was 0.053.⁵ We have also taken this into account in our sample size consideration. Alternative covariance structures for the repeated measures over time will be compared using Akaike's Information Criteria (AIC). This model will be used to test specific hypotheses using contrast statements and to compare temporal changes over time between the intervention and control groups. Variables with baseline imbalances can be incorporated as additional fixed effects. We will also examine a clinically meaningful 30% improvement in PEG from baseline as a binary outcome (yes or no) at each follow-up time point using a logistic mixed effects model incorporating a random effect for class clustering. All analyses will be conducted in SAS version 9.4 with $p < 0.05$ considered statistically significant unless otherwise specified.

Hypothesis 2: patients in OPTIMUM will have significantly improved psychological function at completion of the program and 6- and 12-months later, as compared to PCP Usual Care. Analyses will mirror those described above using a mixed effects model with random effects for the clustering effect of intervention classes and repeated measures on individuals over time, with fixed effects for group, time and their interaction. Contrast statements will be used to compare changes from baseline to specific time points. All analyzes will be conducted in SAS version 9.4 with $p < 0.05$ considered statistically significant unless otherwise specified.

Hypothesis 3: patients in OPTIMUM will be less likely to start and more likely to reduce or stop an opioid prescription for cLBP as compared to those in PCP Usual Care.

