We will examine opioid prescription for cLBP in two ways. First, we will examine the dose of opioids as morphine dose equivalent (continuous outcome) for those subjects with an opioid prescription at baseline. The analytic approach will mirror the mixed models described for Hypothesis 1 to compare group doses over time and in relation to baseline. Next we will use a binary outcome which is yes/no for opioid prescription (any) for each patient at each time point. Analytic methods will again mirror methods for Hypothesis 1 now using a logistic mixed effects model.

Aim 2. To evaluate use of healthcare resources by patients.

Hypothesis: patients in OPTIMUM will have fewer emergency department visits, fewer hospitalizations, fewer imaging (CT/MRI), and fewer procedures (injections, surgery) than PCP usual care.

Healthcare utilization over 6- and 12-months (prescriptions of opioids, injections, surgery, CT/MRI, ED visits, hospitalizations) are mostly in the form of counts. We will fit a series of GEE models with each outcome as the dependent variable, a negative binomial distribution to account for over dispersion, a log link, exposed time period as an offset, intervention arm (OPTIMUM/Usual Care) as the independent factor of interest, and an exchangeable correlation structure for clustering. Alternative correlation structures will be examined via the QIC statistic. Intervention arm incident rate ratios and their significance will constitute the test of the hypothesis.

Aim 3. To evaluate PCP and practice site use of, satisfaction with, and integration of OPTIMUM.

PCP satisfaction with the pain program will be summarized using descriptive statistics and histograms. We will also investigate if these measures are different depending on the demographic characteristics of the PCPs, such as gender, age, race, ethnicity, clinic location, and years since training, or the outcome of the patients using t-test, chi-square test, Pearson or Spearman correlation tests. Number of 8-week programs delivered at each clinic will also be summarized with descriptive statistics. Adoption of EHR tools and OPTIMUM after study completion will be described.

Planned Analysis & Power Assessment

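### The primary PEG model estimates a separate baseline mean in each arm and does not write the T3 contrast on one line; a shared baseline mean would cost nothing and usually tighten the estimate

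*Combined protocol and SAP*

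**What the plan says.** All of this is in the combined protocol and SAP.

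- **Model.** Section 9.6 (Aim 1, Primary Hypothesis) compares PEG at T2, T3 and T4 "with PEG at T1 (baseline) included in the vector of repeated measures using a mixed effects model". It continues "We will include the intervention group indicator, time" and, running on to the next page, their interaction as fixed effects. There is a patient-level random effect and "random class effects for group in the intervention arm". No constraint on the T1 means is stated.
- **Order of events.** Section 6.2.2 places randomization after the baseline measures.
- **Contrast.** "This model will be used to test specific hypotheses using contrast statements"; the same sentence goes on to say that the model will compare the two arms on change over time. Hypothesis 2, whose analysis mirrors this one, is more definite: "Contrast statements will be used to compare changes from baseline to specific time points". The opioid dose analysis is also "to compare group doses over time and in relation to baseline". The power assessment uses an SD of change. Section 9.5.1 names T3 as the primary time point.
- **Other baseline variables.** "We will adjust for any baseline variable that either statistically" (p < 0.2) or clinically differs between arms, and "Variables with baseline imbalances can be incorporated as additional fixed effects".

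**The concern.** Two arms and four visits with group, time and group-by-time give eight free means, two of them at T1. Because T1 precedes randomization, the true T1 means are equal by design. The model therefore estimates a difference that is known to be zero. A contrast in change then subtracts T1 PEG with a slope fixed at 1, whatever the actual T1–T3 relation.

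What is at stake is precision and full specification of the primary test, not validity. With one shared T1 mean, the T3 difference in level and the difference in change become the same quantity, so one edit also settles exactly what is tested. Section 9.6 also leaves open whether T1 PEG itself falls under the p < 0.2 rule, although it is already a response in the model.

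**Working it through.** **The plan's own figures.** Inputs from Planned Analysis & Power Assessment: α = 0.05, SD of change 2.5, ICC 0.053, 10 per class, 20% attrition, difference of 1 point. The design effect is 1 + 9 × 0.053 = 1.477. Two-sided t-test sizes of 100, 114 and 133 per arm, times 1.477 and divided by 0.8, give 184.6, 210.5 and 245.6, which match the table.

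The table inflates both arms, whereas the model has class effects only in the intervention arm. With 225 × 0.8 = 180 per arm, the variance of the change contrast is then 6.25 × (1.477 + 1)/180 = 0.0860. Power for 1 point is 92.5% on 358 df and 90.3% on 22 df (about 23 classes).

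**Precision of the two analyses.** Let s1 and s3 be the T1 and T3 SDs and ρ their correlation.

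- Change contrast, complete data: s1² + s3² − 2ρ·s1·s3 = 6.25 (2.5²).
- Shared-T1 or baseline-adjusted contrast: A = s3²(1 − ρ²).
- The difference between them is B = (s1 − ρ·s3)². It is never negative, and it is zero when s1 = ρ·s3.

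Suppose 225 per arm have T1 and 180 of them also have follow-up. Per arm, the planned change contrast has variance A/180 + B/225, and the shared-T1 contrast has A/180. Add class variance 0.053 × 6.25 = 0.331 at follow-up in the intervention arm, with 8 of each class of 10 retained, and assume that adjustment does not reduce it. This adds 8 × 0.331 = 2.65 on the same scale:

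ratio = (2A + 2.65) / (2A + 1.6B + 2.65)

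**Example, s1 = s3 and ρ = 0.5.** s3² = 6.25, A = 4.6875 and B = 1.5625. The ratio is (9.375 + 2.65)/(9.375 + 2.5 + 2.65) = 12.025/14.525 = 0.828. The interval is 1 − √0.828 = 9% narrower.

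| T1 SD / T3 SD (assumed) | ρ | A | B | Variance ratio | Interval narrower by |
|---|---|---|---|---|---|
| 1.0 | 0.3 | 4.06 | 2.19 | 0.755 | 13% |
| 1.0 | 0.5 | 4.69 | 1.56 | 0.828 | 9% |
| 1.0 | 0.7 | 5.31 | 0.94 | 0.898 | 5% |
| 0.8 | 0.3 | 4.90 | 1.35 | 0.852 | 8% |
| 0.8 | 0.5 | 5.58 | 0.67 | 0.928 | 4% |
| 0.8 | 0.7 | 6.13 | 0.12 | 0.987 | 0.6% |
| 0.6 | 0.3 | 5.69 | 0.56 | 0.940 | 3% |
| 0.6 | 0.5 | 6.17 | 0.08 | 0.991 | 0.4% |
| 0.6 | 0.7 | 6.13 | 0.12 | 0.987 | 0.6% |

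Generalized least squares on all four visits (exchangeable correlation, classes of 10 with 8 followed up) gives the same ratios. Without class variance the ratios are 0.70/0.79/0.88 with equal SDs and 0.82/0.91/0.98 with T1 SD 0.8 of T3 SD, for ρ = 0.3/0.5/0.7.

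**Coding check.** The fixed-effects design for two arms and four visits has rank 8 with group, time and interaction. It still has rank 8 if only the group term is dropped, and rank 7 if both arms share one code at T1. Only the last imposes the constraint.

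**The case against.** A repeated-measures model with group, time and interaction is conventional and defensible. No bias, type I error problem or power failure follows from it. The gain depends on quantities that the documents do not give. Entry requires PEG of at least 3 (Section 4.1), which may restrict the T1 spread, so the equal-SD rows may be optimistic and the true gain could be negligible. All of this stands.

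Three stronger readings are tempting, and the documents support none of them.

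- **That the primary test may be the T3 level difference.** The complete-data ratio would then be 1 − ρ² = 0.91/0.75/0.51 for ρ = 0.3/0.5/0.7, a much larger gain at the higher correlations. But the PEG paragraph itself goes on to speak of comparing change over time between arms, and Hypothesis 2 and the SD of change agree with that. Those gains should not be counted.
- **That baseline PEG is used only if imbalance is seen.** T1 PEG is always in the planned model, and a change contrast always subtracts it. The imbalance rule brings in additional covariates.
- **That the trial is underpowered.** Inflating both arms, as the table does, gives about 87.5% at 225 per arm, but the stated model clusters one arm only and gives 90.3% to 92.5%.

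What the objection does not remove is the direction: in large samples the constrained model is never less precise.

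**Conclusion.** The point holds as an improvement in efficiency and specification. The planned T3 comparison is valid and unbiased, but it leaves each arm's T1 mean free when randomization makes the true means equal. The change contrast at T3 has to be inferred from several places instead of being read from one line.

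Under the assumptions shown, the variance ratio runs from about 0.76 to 0.99 and the interval is about 0.4% to 13% narrower. There is no gain if T1 SD = ρ × T3 SD. The algebra is certain; the size is not, because ρ and the separate SDs are assumed. The change is worth making because it is nearly free, not because the plan fails without it.

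**What to change.** Pre-specify, for PEG, a constrained longitudinal model with one shared T1 mean. Keep T1 in the response vector, give both arms the same treatment code at T1, and allow group terms only at T2, T3 and T4. Deleting only GROUP while keeping GROUP*TIME changes nothing.

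Alternatively, take T1 out of the responses and model T2–T4 with T1 PEG and T1-by-time as covariates. This is close but not identical, because participants with baseline only drop out.

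Then state that:

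- the group contrast at T3 from this model is the primary test;
- T1 PEG is handled this way whatever imbalance is observed, so the p < 0.2 rule covers only other baseline variables;
- the PROMIS-29 Mental Health analysis takes the same form.

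The cost is a recoded variable (or two covariate terms) in the SAS code and two or three SAP sentences. No new data are needed.

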Life Events Checklist for DSM-5 (LEC-5), *This form will be asked once at any upcoming timepoint (including monthly assessments)		*	*	*	17
Global Mindfulness				X	13
EHR Outcomes					
Opioid prescriptions and other prescriptions for pain, CT/MRIs of lumbar-sacral spine, injections of lumbar-sacral spine, ED/urgent care visits for LBP, Surgeries of lumbar spine, hospitalizations for LBP, PCP visits for LBP, physical therapy referrals for LBP	X		X		X
Core HEAL Pain Data Measures					
PROMIS Physical Function (questions 1-4 same as in PROMIS 29 questions 1-4)	X		X		2 additional questions
PROMIS Sleep (questions 1-4 same as in PROMIS 29 questions 17-20)	X		X		2 additional questions
Sleep Disturbance	X		X		2
Depression PHQ-2	X		X		2
Anxiety GAD-2	X		X		2

*Primary Timepoint **Primary outcome.

Pain impact is defined as Pain intensity, pain interference and functional status calculated from 9 items of the PROMIS-29. PROMIS: patient reported outcomes measurement information system.

Yellow Highlight=Core HEAL Measures incorporating into OPTIMUM outcomes.

Additional Baseline Variables: We will assess age, sex, race, ethnicity, and socioeconomic status, involvement in workers' compensation, work status, previous treatment including nonpharmacological therapies, and marital and educational status. Biomedical factors will include: a) comorbidity: data on comorbidity will be gathered using the Charlson Co-Morbidity Index T1;⁶⁰ b) pain medications (regularly scheduled and as-needed) at T1-T4 and will be categorized into sub-classes: i) salicylates (aspirin > 1200 mg/day, salsalate); ii) non-aspirin, non-COX2 selective NSAIDs; ii) COX2 selective NSAIDs; iv) acetaminophen; v) opioids; vi) skeletal muscle relaxants; vii) adjunctive agents (e.g., corticosteroids, capsaicin, Neurontin); and c) antidepressants and antianxiety medications. Regularly scheduled opioid analgesics will be converted to daily oral morphine equivalents.⁶¹

Randomization

To ensure balance between groups, we will use permuted block randomization with block size of 4 or 6, in a 1:1 ratio, stratified by clinic and sex. Participants will be randomized after completion of baseline measures.

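### Section 9.6 gives the OPTIMUM class random effect no time index and leaves the primary T3 contrast unwritten; coded as a constant intercept, the effect cancels from a T1-to-T3 change contrast

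*Combined protocol and SAP*

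**What the plan says.** Section 9.6 (Aim 1, Primary Hypothesis) compares PEG at T2, T3 and T4 "with PEG at T1 (baseline) included in the vector of repeated measures using a mixed effects model". Fixed effects are group, time and their interaction. The random part is described as "with random effects for repeated measures on individuals over time and random class effects for group in the intervention arm". The stated purpose is: "We are proposing to control for clustering effect within each class using a random effect". This control is said to be needed "because the response of participants in the same class might be correlated". Nothing says whether the class effect is one intercept for all visits, acts only at follow-up, or varies by time.

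The primary contrast is not written out. The model is to be used with contrast statements and "to compare temporal changes over time between the intervention and control groups". Hypothesis 2, whose analysis mirrors this one, adds: "Contrast statements will be used to compare changes from baseline to specific time points". The AIC step does not settle the class effect, because it is confined to the person-level structure: "Alternative covariance structures for the repeated measures over time will be compared using" that criterion.

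Section 6.2.2 fixes the timing of T1: "Participants will be randomized after completion of baseline measures". The power text in section 9.6 uses an SD of change of 2.5, an ICC of 0.053, 10 patients per class and 20% attrition.

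**The concern.** T1 PEG is recorded before randomization, so at T1 nobody has met their class. Correlation produced by sharing a class can only appear from T2 on. A random effect with no time index is most simply coded as one value per class added to every visit, T1 included. In a T1-to-T3 change that value is subtracted from itself. The model output would list a class variance, yet the standard error of the primary contrast would carry no class design effect.

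At stake is the primary interval, which would be too narrow, and a type I error above the nominal 5%. It would also be an internal mismatch: the sample size allows for class clustering of change, and the test would not.

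**Working it through.** **1. The plan's own sample size.** Inputs are those of the power text; a two-sided test at 0.05 reproduces the table.
- Design effect: 1 + (10 − 1) × 0.053 = 1.477.
- Two-sample t-test n per arm for a 1-unit difference at 80, 85 and 90% power: 100, 114, 133.
- Multiplied by 1.477 and divided by 0.80: 184.625, 210.47 and 245.551, as tabulated. All 15 rows agree to within 0.001.
- At 225 per arm: 225 × 0.80 / 1.477 = 121.9 effective, power 87.7%, consistent with the plan's claim.

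So the design applies the ICC to an SD of change, and inflates both arms.

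**2. What happens to the class effect.** Let u be the effect of a patient's class.
- Constant intercept: the T3 − T1 change contains u − u = 0.
- Follow-up-only effect: the change contains u.

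Take 22 classes of 10, 220 controls, a person-level SD of change of 2.5 and class variance 0.053 × 6.25 = 0.331. The standard error of the between-arm difference in T3 − T1 is:
- no class term: 2.5 × √(2/220) = 0.2384;
- constant class intercept: 0.2384;
- follow-up-only effect: √(0.2384² + 0.331/22) = 0.2681.

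With 20% lost after T1 (assuming SD 2.5 at each visit and within-person correlation 0.5), the three become 0.2607, 0.2609 and 0.2889. The cancellation is exact with complete data and nearly exact with dropout.

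If the T3 group difference alone is tested, nothing cancels: with the class variance known, the constant intercept also gives 0.2681.

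**3. Size.** With clustering in one of two equal arms and m evaluable per class, DE = 1 + (m − 1) × 0.053, the SE ratio is √(2/(1 + DE)), and type I error is 2Φ(−1.96 × ratio). Section 5.1 gives classes of about 5 to 12; 20% is removed for attrition. The 8-per-class row is Appendix D's 24 OPTIMUM patients per cohort over three sites, assuming one class per site: 24/3 = 8, and 8 × 0.80 = 6.4.

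| Enrolled per class | m | DE | SE ratio | Type I, closed form | Type I, simulated, T3 − T1 | Type I, simulated, T3 alone |
|---|---|---|---|---|---|---|
| 5 | 4 | 1.159 | 0.962 | 5.9% | 6.2% | 5.6% |
| 8 | 6.4 | 1.286 | 0.935 | 6.7% | 6.9% | 5.9% |
| 10 | 8 | 1.371 | 0.918 | 7.2% | 7.2% | 6.4% |
| 12 | 9.6 | 1.456 | 0.902 | 7.7% | 7.8% | 6.2% |

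The simulated columns use the constant intercept, 45, 28, 22 and 19 OPTIMUM classes, an equal control arm, 20% losing T2–T4 at random, variance 6.25 per visit, within-person correlation 0.5 and class variance 0.331 at T2–T4 only. Rejection rates are z-tests on 20,000 data sets at the mean fitted covariance (Monte Carlo error about 0.2 points). Mean fitted T3 − T1 standard errors with and without the constant intercept were the same to within 0.0001 (for example 0.2568 v 0.2569 at 8 per class, against an empirical SD of 0.2769).

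A smaller simulation, refitting by REML on 1,500 complete data sets with 22 classes of 10, gave 7.0% for the constant intercept and 4.1% for the follow-up-only effect. The constant coding estimated the class variance at 0.18 on average, against a true 0.331. That dilution, from including T1, explains the excess in the T3-alone column.

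**4. Sensitivity over the four class sizes.**
- ICC of change 0.02: 5.3–6.0%. ICC of change 0.01: 5.2–5.5%.
- Half of the ICC already present at T1 (illustration): 5.9% at m = 6.4 and 6.6% at m = 9.6.

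**5. The remedy.** In the 20,000-data-set simulation the follow-up-only effect gave 5.2%, 5.2%, 5.0% and 4.9%. That is slightly idealised. Re-estimating the variance in each data set (change scores, z-test) gave 5.2%, 5.0%, 5.4% and 5.7% for 45×4, 28×6, 22×8 and 19×10, with the class variance estimated as zero in 15–25% of runs. Hence the need for a stated degrees-of-freedom method.

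**The case against.** The strongest reply is that the documents contain no faulty model. Section 9.6 says class clustering will be controlled, and its wording is compatible with a follow-up-only or class-by-time effect. A reader might infer that the planned primary standard error omits clustering; the text does not commit to that. The contrast is also open. Comparing PEG at each follow-up visit, and powering for a difference in PEG between groups, both allow a test of the T3 difference alone. This part of the reply stands: the point is an under-specification with a consequence under one reading, not a demonstrated error.

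It does not reduce the point to a request for detail. References to temporal changes, changes from baseline and an SD of change all lean towards T3 − T1. A single constant intercept is the plainest coding of an unindexed random effect. The two codings give different primary p-values, and nothing in the AIC step would choose between them.

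The second reply concerns size. The upper figures need class correlation that arises only after T1 and an ICC of 0.053 that applies to change. The plan describes the source of that ICC in two different ways and does not say whether it refers to change or to a single visit. Some class correlation at T1 is plausible if classes form within sites, and removing that part from a change score is correct. The 7.2–7.7% figures also need classes of 10 to 12, more than Appendix D suggests. All of this stands and is carried into the ranges.

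**Conclusion.** The point holds as a conditional one and should be fixed before analysis. The primary standard error loses the class design effect if the class effect is coded as constant and the T1-to-T3 change is tested. If, in addition, class correlation arises after T1 and the ICC of change is 0.053, two-sided type I error is about 6–8%, and about 6.7% at the class size the schedule suggests. Lower ICCs of change, or correlation already present at T1, shrink it as shown above.

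Two stronger readings are not supported. The documents do not show that the sponsor will fit the constant intercept. Nor does the class effect cancel if only the T3 difference is tested; the smaller understatement there comes from the diluted variance estimate.

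The Hypothesis 2 model and the opioid models that mirror Hypothesis 1 have the same gap. Its size there is unknown, because no ICC is given for those outcomes. The cancellation does not affect the 30%-improvement logistic model, whose outcome is defined only at follow-up.

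**What to change.** In section 9.6:
- Write out the primary contrast, for example the between-arm difference in PEG change from T1 to T3.
- State that the OPTIMUM class random effect is zero at T1 and acts on T2–T4, or add a class-by-time effect.
- Name a small-sample degrees-of-freedom method.
- Apply the same to Hypothesis 2 and to the continuous and binary opioid models.

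This costs a few sentences and one changed RANDOM statement. Under the assumptions above the interval widens by about 4% at 4 evaluable per class (1/0.962) to 11% at 9.6 (1/0.902). No extra patients are needed. At 180 evaluable per arm and 10 per class, clustering in one arm gives a standard error of 2.5 × √((1 + 1.477)/180) = 0.293. The power table, which inflates both arms, implies 2.5 × √(2 × 1.477/180) = 0.320. Power for a 1-unit difference at 0.293 is about 93%.

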1. STUDY OBJECTIVES

1.1 Primary Objective

Specific Aims of the study are:

Aim 1: To integrate and test an evidence-based mindfulness clinical pain program, OPTIMUM, for patients with cLBP in the primary care setting.

Primary Hypothesis: Patients in OPTIMUM will have significantly improved pain intensity and interference as measured by the PEG composite score at completion of the program and 6 months (primary end point) and 12-months later, as compared to PCP Usual Care.

Hypothesis 2: Patients in OPTIMUM will have significantly improved psychological function as measured by the PROMIS-29 Mental Health Summary Scale at completion of the program and 6-and 12-months later, as compared to PCP Usual Care.

Hypothesis 3: Patients in OPTIMUM will be less likely to start and more likely to reduce or stop an opioid prescription for cLBP as compared to those in PCP Usual Care.

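### Hypothesis 3 predicts fewer opioid starts and more stops, but the pooled yes/no model measures only net prevalence: starting has no dedicated test and stopping at most an indirect one

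*Combined protocol and SAP*

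**What the plan says.** Section 1.1 states Hypothesis 3: "Patients in OPTIMUM will be less likely to start and more likely to reduce or stop an opioid prescription for cLBP", compared with usual care. Sections 9.1 and 9.6 repeat it.

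Section 9.6 plans two analyses.

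- **Dose.** Morphine-equivalent dose as a continuous outcome, "for those subjects with an opioid prescription at baseline", in mixed models used "to compare group doses over time and in relation to baseline".
- **Yes/no prescription.** "a binary outcome which is yes/no for opioid prescription (any) for each patient at each time point". On the model: "Analytic methods will again mirror methods for Hypothesis 1 now using a logistic mixed effects model".

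The Hypothesis 1 model has fixed effects for group, time and their interaction, and random effects for patient and for class in the OPTIMUM arm. The baseline value is one of the repeated outcomes. No term separates patients who had a prescription at baseline from those who did not. The rule for adjusting for baseline differences (p < 0.2 or clinically relevant) could add a covariate, but it would not split the treatment effect.

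**The concern.** Starting, reducing and stopping are transitions, and each is possible only from one baseline state. A patient without a prescription at baseline can start but cannot stop; a patient with one can reduce or stop but cannot start. The dose model covers only the second group. The yes/no model covers everyone and returns one treatment effect per time point.

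Two things are at stake. A real gain confined to stopping, or to starting, can be lost when averaged with patients in whom nothing changed. And a favourable pooled result could be reported as fewer starts or as more stops although the analysis supports neither attribution. Opioid use is a named Aim 1 hypothesis and part of the trial's stated rationale, so readers will want to know which of the two happened.

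**Working it through.** **Inputs from the documents.** 225 per arm (section 9.2); alpha 0.05, 20% attrition, ICC 0.053 and 10 per class (section 9.6, power assessment). Completers per arm: 225 × 0.80 = 180.

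**The plan's own figure.** The only power calculation concerns the PEG, and it reproduces. A two-sided t-test for a 1-unit difference with SD 2.5 at 80% power needs 100 per group; 100 × (1 + 9 × 0.053) / 0.80 = 100 × 1.477 / 0.80 = 184.625, as tabulated. No figure is given for Hypothesis 3, so there is nothing to reproduce for this point.

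**What the pooled contrast estimates.** Let b be the proportion with a baseline prescription, s the start rate among non-users and q the stop rate among users. Follow-up prevalence in an arm is

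P = (1 − b)·s + b·(1 − q),

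so the arm difference (OPTIMUM minus usual care) is

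ΔP = (1 − b)·(s₁ − s₀) − b·(q₁ − q₀).

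One number cannot identify two differences. This holds whatever the rates are.

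**Illustration A.** Assumed, not in the documents: b = 25%, starts 5% in both arms, stops 10% under usual care and 25% under OPTIMUM.

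- Usual care: 0.75 × 0.05 + 0.25 × 0.90 = 26.25%
- OPTIMUM: 0.75 × 0.05 + 0.25 × 0.75 = 22.5%
- ΔP = −0.25 × 0.15 = −3.75 points, so a 15-point effect on stopping shows as under 4 points.

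Power from 20,000 simulated trials, rejecting at z < −1.96, before class clustering:

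| Per arm | Pooled, crude | Pooled, stratified by baseline use (Mantel-Haenszel) | Stop test in baseline users |
|---|---|---|---|
| 225 | 15% | 31% | 56% |
| 180 | 13% | 26% | 48% |

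**Illustration B, range of baseline use.** Assumed: usual-care starts 10% and stops 20%; OPTIMUM starts 5% and/or stops 40%; 180 per arm; normal approximation; crude pooled test; no clustering.

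| b | Only stopping improves: pooled / direct | Only starting improves: pooled / direct | Both improve: pooled |
|---|---|---|---|
| 20% | 15% / 46% | 15% / 36% | 48% |
| 30% | 24% / 62% | 11% / 32% | 54% |
| 40% | 36% / 75% | 9% / 29% | 61% |

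**Closer to the planned model.** A group × time logistic GEE with baseline in the outcome vector (400 replicates, b = 30%, a marginal stand-in for the mixed model) rejects in 32% of trials if only stopping improves, 17% if only starting improves, and 69% if both do. Using baseline in this way recovers some power but still reports only a net change.

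**The case against.** The strongest reply is that the plan does more than the yes/no model suggests, and that pooling suits the hypothesis as written. Much of this stands.

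- **A reader might infer that no part of Hypothesis 3 is tested.** The documents do not support that. The dose model in baseline users tests reduction, and it captures stopping if a stopped prescription counts as dose zero. That coding is not stated, which is why stopping is tested at most indirectly.
- **A reader might infer that effects on starting and stopping generally cancel.** In the hypothesised direction s₁ − s₀ is negative and q₁ − q₀ is positive, so both terms of ΔP are negative and add. Cancelling requires OPTIMUM to help one part and harm the other. With b = 25%, 225 per arm, stops 10% to 25% and starts 8% to 4% (assumed), the baseline-stratified pooled test has about 73% power, against 57% for the stop test and 34% for the start test. This is a good reason not to replace the pooled model.
- **A reader might infer that morphine equivalents omit as-needed opioids**, from the sentence "Regularly scheduled opioid analgesics will be converted to daily oral morphine equivalents". That sentence belongs to the additional baseline variables. Section 6.2.2 also says that the EHR will assess opioids from prescriptions written and will treat cumulative exposure as morphine equivalents, without that limit. Section 9.6 does not tie the dose model to the narrower conversion, so at most a cross-reference is missing.
- **A reader might infer that the yes/no outcome ignores indication.** Section 9.6 introduces both analyses as concerning prescriptions for cLBP, and *any* may mean any drug or dose. However, the EHR row of Table 2 qualifies visits, hospitalizations and physical therapy referrals as for LBP and does not so qualify opioid prescriptions. The text leaves the matter open.

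What the reply does not answer is that no analysis is restricted to patients who could start, and no outcome is defined as stopping.

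**Conclusion.** The point holds in this scope: the pooled model tests net prevalence, starting has no dedicated test, stopping is tested at most indirectly through the dose model, and an effect on only one of them is diluted. The identification problem follows from the outcome definition and needs no assumed rates.

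The size of the power loss does depend on assumptions. Where only one part changes, the pooled test has roughly a quarter to a little over half the power of the direct test across the scenarios shown. All of these rest on assumed baseline use and start and stop rates, and ignore class clustering, which would lower power further. Where both parts change as hypothesised, a pooled test that accounts for baseline use is the stronger one. This is a gap in a secondary hypothesis that should be closed; it does not touch the primary PEG comparison.

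**What to change.** Keep the dose model and the pooled yes/no model, and make these additions to section 9.6.

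1. Prespecify two analyses by arm, each with the class random effect in the OPTIMUM arm: (a) a new opioid prescription during follow-up among patients with none at baseline; (b) no opioid prescription at follow-up among patients with one at baseline. A group × time × baseline-use model with contrasts within each stratum would do the same. If that route is taken, fit it to the follow-up time points, because baseline use cannot be both a stratum and an outcome.
2. State that an effect will be attributed to starting only from (a) and to stopping only from (b). The pooled result is to be described as net prevalence.
3. In the dose model, code dose as zero after a prescription stops, so that patients who stop stay in the comparison.
4. Reconcile *for cLBP* with *any*: say whether the yes/no outcome is limited by indication, and if so how the EHR identifies it.
5. Say that (a) and (b) are secondary, and whether any multiplicity adjustment applies.

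The cost is SAP wording and two models on EHR data that the plan already extracts, with no new data collection or patient burden. The downside is that each subgroup is smaller than the full sample and two secondary tests are added, so the estimates should be reported with confidence intervals and their limited power acknowledged.
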